# Statistical Analysis Plan

In order to verify hypothesis stated in this research, statistical analysis will be conducted using IBM SPSS v. 25 and Jamovi v1.2.8. Frequency distribution analysis, basic descriptive statistics with Shapiro-Wilk's test for normality of distributions, *t*-tests for independent samples, two-way independent mixed ANOVAs as well as chi-squared tests of independency will be computed.

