## PURPOSE

The aim of the study is to compare the advantages of SEP and SLP positioning during bottle-feeding of preterm infants  $\leq 34$  weeks gestational age.

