## METHOD

The study will include forty two neonates ( $n=42$ ) born  $\leq 34$  weeks of gestational age. Four bottle-feeding sessions will be tested in each of the newborn: two in the SEP and two in the SLP. The position for the first study will be randomly assigned, then positioning will be changed after each feeding session. In one day, only two consecutive feeding sessions which will be included to the study in order to minimize fatigability as a disrupting factor. The levels of saturation ( $SpO_2$ ) and heart rate (HR) will be measured as the parameters indicative of the newborn's physiological stability. The factors determining the qualitative aspects of feeding included the total time of declines of  $SpO_2 \leq 85\%$ , level of the newborn's alertness according to the Neonatal Behavioral Assessment Scale (NBAS), and the occurrence of choking episodes. The proportion of milk consumed (volume of milk eaten relative to the expected volume) and the duration of the feeding and feeding session will be also recorded.

Each feeding session will be recorded with a video camera. It should be mentioned that participation in the study will not oblige the parents to use any of the positions which will be used during the study and to bottle-feeding. Bottle-feeding will be continued with attempts of the breastfeeding, if only it will be possible.

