## STUDY DESIGN

The study is designed as a crossover study - alternate study. It will be a randomized trial. Each infant will be bottle-fed four times: twice in the SEP and twice in the SLP. In each of the study positions 84 feeding sessions will be analyzed (total amount of feeding sessions which will be analyzed will be 168). The position for the first trial will be randomly assigned (random table), then positioning will be changed after each feeding session. The study will include observation of the newborn before, during and after the feeding and the following measurements:

- A. 2 minutes before the feeding session: oxygen saturation ( $SpO_2$ ) level, heart rate (HR) (pulse oximeter data), alertness level
- B. 3rd minute of the feeding session:  $SpO_2$ , HR, alertness level
- C. 10th minute of the feeding session:  $SpO_2$ , HR, alertness level, volume of food eaten
- D. the end of the feeding session:  $SpO_2$ , HR, alertness level, volume of food eaten
- E. 10 minutes after the feeding session:  $SpO_2$ , HR, alertness level

The declines of  $SpO_2 \leq 85\%$  level, total time of feeding and feeding session, occurrence chocking episodes also will be recorded.

During the study feeding, normal feeding session procedures will be applied: avoidance of excessive stimuli by ensuring calm environment with limited level of light and noise, pauses in the feeding after a series of suckling (interval feeding), manual support within the articulation apparatus to improve lip tightness and/or mandibular function. Stimulation of the suction reflex will be also allowed.

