## WHAT WILL BE ANALYZED?

- Differences in changes in blood oxygen saturation due to the position of the baby during feeding
- Heart rate variations due to the position of the baby during feeding
- Differences in the change in baby's activity due to the baby's position during feeding
- The position of the baby during feeding and choking episodes
- Differences in the proportion of the volume of eaten food due to the position of the child during feeding
- Differences in feeding times and feeding sessions due to the position of the baby during feeding
- Differences in the time of saturation decrease to the level of  $\leq 85\%$  due to the position of the child during feeding

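### Eight outcomes are to be tested at equal rank, with no primary outcome, significance level, multiplicity rule or exploratory label, so a claim of advantage could rest on any one of them

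*Combined protocol and SAP*

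**What the plan says.** The PURPOSE section gives a general aim and names no outcome: "The aim of the study is to compare the advantages of SEP and SLP positioning".

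The Statistical Analysis Plan opens with "In order to verify hypothesis stated in this research". Besides descriptive statistics and normality checks, it names independent-samples t-tests and "two-way independent mixed ANOVAs as well as chi-squared tests of independency will be computed". It attaches no significance level, sidedness or correction to any of them.

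The section WHAT WILL BE ANALYZED? has seven bullets in no stated order of importance: oxygen saturation, heart rate, activity (alertness), choking, proportion of milk eaten, feeding and session times, and time at saturation of 85% or less. One bullet holds two outcomes: "Differences in feeding times and feeding sessions due to the position of the baby during feeding". METHOD confirms that these are separate durations: "the duration of the feeding and feeding session will be also recorded". Seven bullets therefore cover eight outcomes.

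METHOD sorts the measures into physiological stability, a qualitative group ("The factors determining the qualitative aspects of feeding included the total time of declines of" saturation, alertness and choking) and measures also recorded. This is a grouping by kind, not a ranking.

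STUDY DESIGN gives the size in sessions: "In each of the study positions 84 feeding sessions will be analyzed", 168 in total. It places saturation, heart rate and alertness at five measurement points, A to E.

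**The concern.** A randomised comparison that sets out to verify a hypothesis needs to say in advance which result would support it. Here eight results stand side by side, either position may come out ahead on any of them, and nothing states how many must agree or which one counts. A reader of the eventual report could not tell a single chance finding among eight from a planned test that succeeded.

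Two things are at stake. The first is the error rate: reading one significant result among eight as an advantage carries more risk of a false claim than one test does. The second is that the comparison has no defined success or failure, so the weight given to each outcome can be settled after the results are known.

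**Working it through.** **1. The plan's own figures.** 42 infants × 4 sessions = 168, and 42 × 2 = 84 per position. Both agree with STUDY DESIGN. The choice of 42 cannot be reproduced, because no significance level, power, effect size or standard deviation is given.

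**2. Number of tests.** Seven bullets, one holding two outcomes, give 8. This is a minimum. If the mixed ANOVAs supply both a position test and a position-by-time test for saturation, heart rate and alertness, the count is 8 + 3 = 11.

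**3. Chance of at least one false difference.** Assumptions: no true difference on any outcome, and one valid two-sided 5% test per outcome.

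- Independent outcomes: 1 − 0.95^8 = 0.337. For seven tests, 1 − 0.95^7 = 0.302. For eleven, 1 − 0.95^11 = 0.431.
- Eight normal test statistics with common correlation ρ: 1 − ∫ φ(u) [Φ((1.96 − √ρ·u)/√(1−ρ)) − Φ((−1.96 − √ρ·u)/√(1−ρ))]^8 du. This gives 0.250 at ρ = 0.5 and 0.191 at ρ = 0.7.
- The level is itself assumed. With eight independent tests the figure is 1 − 0.99^8 = 0.077 at a 1% level and 1 − 0.90^8 = 0.570 at 10%.

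The documents give no correlations. Feeding time and session time overlap, and time at 85% or less comes from the same saturation signal, so the correlated figures are the more relevant ones.

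**4. Whether a multiplicity rule alone would be enough.** It would not, because Holm controls error only if each test holds its level. Simulation: 42 infants × 2 positions × 2 sessions, normal outcome, all nulls true, each p-value compared with 0.05/8 = 0.00625. The variance shares are illustrative and do not come from the documents. The overall rate is 1 − (1 − per-test rate)^8.

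| Variance shares | Test | Per-test rate | Overall, 8 independent outcomes |
|---|---|---|---|
| Infant 10%, infant-by-position 20% | independent-samples t | 0.0094 | 0.072 |
| Same | paired t on infant means | 0.0063 | 0.049 |
| Infant 30% only | independent-samples t | 0.0012 | 0.010 |
| Same | paired t on infant means | 0.0062 | 0.049 |

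The independent-samples test can err in either direction. The paired test holds its level in both cases.

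**5. Cost in power of Holm.** Paired t-test, 42 infants, 41 degrees of freedom. The difference detectable with 80% power is 0.443 SD of the within-infant difference at 0.05 and 0.578 SD at 0.00625. Power for 0.443 SD at 0.00625 is 0.50.

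**6. Choking.** In a two-sided paired permutation test, infants with equal counts in both positions contribute nothing. With m unequal infants the smallest possible p-value is 2/2^m: 2/256 = 0.0078 for m = 8 and 2/512 = 0.0039 for m = 9. The threshold of 0.00625 is out of reach below m = 9.

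**7. Primary outcome plus Holm on the other seven.** If the seven are tested whatever the primary shows, the overall rate under independence is 1 − 0.95 × (1 − 0.05/7)^7 = 0.096. If they are tested only after a significant primary, it stays at 0.05.

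**The case against.** The strongest reply is that this rests on a reading of intent. Verifying a hypothesis is a stock phrase at the head of a one-paragraph plan, the stated aim is only to compare advantages, and nowhere does the plan say that one significant result will decide for a position. The list of analyses is also fixed in advance, which limits selective reporting. Much of this stands. A reader might infer that the sponsor intends to claim an advantage from any single positive result; the documents do not say so. They only fail to exclude it. Nor does the plan take the exploratory route: it announces hypothesis tests and carries no such label.

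A reader might also infer that the study has no hypothesis. That is not supported: the plan refers to one as stated, and part of the document was not available to check. No weight rests on that point here.

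A third tempting reading is that the plan as written has a 34% error rate. It does not follow. That figure needs an assumed 5% level, valid tests and eight independent outcomes. The outcomes overlap, and the planned tests treat repeated sessions from one infant as independent, so their actual rate is unknown and could be higher or lower.

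**Conclusion.** The concern holds in a limited form. The plan tests eight outcomes at equal rank and provides nothing in the available text to say which result decides, at what level, or with what correction. For valid two-sided 5% tests, the chance of at least one false difference is about 19% to 25% at correlations of 0.7 to 0.5. The values of 34% for eight tests and 43% for eleven belong to independence and are better seen as the upper end. All these figures depend on the assumed level and on tests that respect the pairing within infants; none of them describes the planned independent-samples tests.

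This is something the sponsor should correct before analysis. It does not show that the comparison itself is unsound, since the crossover data allow a valid within-infant test of every outcome.

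**What to change.** Before any data by position are seen:

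1. State the significance level, for example two-sided 5%.
2. Fix one position contrast per outcome. For saturation, heart rate and alertness, this could be the session's mean over measurements B to D minus measurement A, with position-by-time results reported descriptively.
3. Test each contrast within infant, by a paired comparison of the infant's two-session mean in SEP and in SLP. For choking, use a paired permutation test on each infant's number of sessions with choking.
4. Choose one rule:
   - (a) Holm across the eight outcomes at 5% overall, first threshold 0.00625; or
   - (b) one outcome, named by the sponsor from those planned for collection, as primary at 5%. The other seven are reported as estimates with confidence intervals, or tested by Holm only if the primary is significant.
5. If the study is meant as exploratory, say so instead, and report all eight as estimates with confidence intervals and no confirmatory claim.

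The cost is SAP wording and a change of analysis method. No new data are needed, because each infant is already fed twice in each position. Under (a), the detectable difference at 80% power rises from 0.44 to 0.58 SD, and an effect with 80% power at 5% has about 50% at the first threshold. Power for choking may be much lower, since at least 9 infants must have unequal counts before that threshold can be reached. Option (b) allows fewer confirmatory claims, and the exploratory route allows none.

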## INCLUSION CRITERIA

- circulatory and respiratory stability;
- readiness for oral feeding according to each child's Speech-Language Pathologist assessment;
- prematurely born infants who were in the process of being transferred from enteral nutrition (or enteral nutrition + parenteral nutrition) to full

- oral feeding and were fed orally at least 4- 6 times within twenty-four hours;
- parents gave informed consent to participate their infant in the study.

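### Time at SpO2 of 85% or less would, on the natural reading, go to an unpaired t-test; a pre-specified within-infant signed-rank test suits the crossover and the likely skew better, with a power gain that depends on assumptions.

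*Combined protocol and SAP*

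**What the plan says.** The Statistical Analysis Plan lists "basic descriptive statistics with Shapiro-Wilk's test for normality of distributions", then t-tests "for independent samples, two-way independent mixed ANOVAs" and chi-squared tests. It attaches no decision to the Shapiro-Wilk result and lists no rank-based, transformed, bootstrap or two-part method.

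The list of analyses includes "Differences in the time of saturation decrease to the level of" 85% or below, by position. No test is assigned to this or any other outcome.

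The design is a randomised crossover. Under Study Design, "Each infant will be bottle-fed four times: twice in the SEP and twice in the SLP", and "In each of the study positions 84 feeding sessions will be analyzed". Eligibility requires "circulatory and respiratory stability". The documents state no alpha, power, effect size or within-infant correlation, and nothing about the distribution of this outcome.

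**The concern.** A normality test with no stated consequence leaves the analyst two options when it rejects: ignore it, or pick another method after seeing the data. Neither is a plan.

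The gap matters most for time at SpO2 of 85% or less. A duration cannot be negative. In infants judged stable enough to feed orally, some sessions may well score zero while a few run long. The eligibility criterion makes zeros plausible but does not establish how many there will be.

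Of the listed tests, the independent-samples t-test is the natural one for a single continuous value per session in two positions. It treats the sessions as 168 unrelated observations, although each infant serves as its own control. Its variance is also driven by the longest desaturations. With 42 infants and no power calculation, a real position effect could be missed and the non-significant result read as showing no difference.

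**Working it through.** **Plan's own figures.** 42 infants × 2 sessions = 84 per position; 42 × 4 = 168 in total. Both reproduce. There is no stated power to reproduce.

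**Assumed inputs, because the documents give none.** Two-sided 5% level. Probability of any time at or below 85% in the reference position of 0.3, 0.5 or 0.7 for a typical infant, with infant SD 1 on the logit scale; this gives about 67%, 50% and 33% zero sessions. Non-zero times lognormal with median 20 s, infant log-SD 0.6 and session log-SD 1.2 (heavy tail) or 0.8 (milder tail).

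**Tests compared.** Independent t-test on 84 against 84 sessions; paired t-test and Wilcoxon signed-rank test on the 42 differences, d = infant's mean time in one position − mean time in the other.

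**Power by simulation** (67% / 50% / 33% zero sessions):

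| Assumed position effect | Session log-SD | Independent t | Signed-rank | Gain, points |
|---|---|---|---|---|
| Odds of any desaturation and duration both halved | 1.2 | 44 / 56 / 64% | 64 / 77 / 85% | 20 / 21 / 21 |
| Both halved | 0.8 | 70 / 85 / 92% | 79 / 93 / 98% | 9 / 8 / 6 |
| Duration only halved | 1.2 | 19 / 31 / 42% | 24 / 40 / 57% | 5 / 9 / 15 |
| Duration only halved | 0.8 | 35 / 56 / 76% | 38 / 63 / 86% | 3 / 7 / 10 |

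The first two rows use 3000 trials per setting and the last two use 2000. The largest simulation standard error is √(0.25/3000) = 0.9 points or √(0.25/2000) = 1.1 points.

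**Type I error in this model.** 2.4–3.3% for the independent t-test and 4.5–5.2% for signed-rank.

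**Role of pairing alone.** In the heavy-tail setting with both effects, the paired t-test gives 44 / 56 / 64%, no better than the unpaired test. The assumed within-infant correlation there is weak: on the log scale 0.6² / (0.6² + 1.2²) = 0.36 / 1.80 = 0.20. With infant log-SD 1.2, logit SD 2 and session log-SD 0.8, it is 1.44 / (1.44 + 0.64) = 0.69, and pairing alone raises power from 45% to 57% (50% zeros). Signed-rank is higher still.

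**A second model as a sensitivity check.** The infant effect was entered as a latent correlation of 0 or 0.4, with 14 non-null settings at each value (0 to 85% zeros, log-SD 0.5 to 1.5).

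- At correlation 0.4, signed-rank beat the independent t-test in all 14 settings, by about 6 points (0.294 to 0.350) to 39 points (0.369 to 0.762). The independent t-test's type I error was 1.0–1.5%.
- At correlation 0, the difference ran from about −5 points (0.318 to 0.271; 70% zeros, duration-only effect) to +27 points (0.353 to 0.619).

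**A wider grid.** In 72 non-null settings (500 trials each), signed-rank was ahead in all but one near-tie (18% against 19%), by up to 47 points. Across the grid, type I error was about 4–7% for signed-rank and 0.4–5% for the independent t-test.

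**The case against.** The strongest objection is that every power figure rests on assumed inputs. This stands. It is why the loss has to be given as a range, and a reader who infers a uniformly large loss goes further than the documents allow. With a mild tail, many zeros and an effect on duration only, the gain is about nil. With no within-infant correlation at all, the signed-rank test can be slightly worse.

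Other stronger readings also fail:

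- *Every listed test is parametric.* Chi-squared tests are listed too, so the statement holds only for continuous outcomes.
- *The plan assigns a t-test to this outcome.* It assigns no test to any outcome; the t-test is an inference.
- *The planned test gives false positives.* In the null settings run it was at or below about 5%, and often well below.
- *Pairing gains nothing.* That is true only when within-infant correlation is weak.
- *Any rank test would do.* A Mann-Whitney test on 84 against 84 sessions still ignores pairing and can lose badly. At correlation 0, log-SD 1, 50% zeros and duration halved, its power was 0.20 against 0.56 for the t-test.
- *A sign-flip permutation test on the mean difference is equivalent to signed-rank.* It stays sensitive to the tail: at log-SD 1.2 and 50% zeros, power was 57% for paired t, 66% for sign-flip and 76% for signed-rank.

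A further objection stands. The signed-rank test down-weights long desaturations, which may be the clinically important ones. At log-SD 1.2 with 30% of sessions showing desaturation, the median Hodges-Lehmann estimate was 2.4 s against a mean difference of 10.6 s; at 15% it was 0 s against 5.4 s. A rank-based estimate alone would therefore mislead.

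**Conclusion.** The point holds in a limited form. Normality is tested with no stated consequence. The natural choice among the listed tests for this outcome ignores the pairing and is sensitive to a few long sessions. A signed-rank test on the 42 within-infant differences is generally the more powerful choice: by about 0 to 20 points under the first model, and more when infants differ strongly. Losses of up to about 5 points appeared only with zero within-infant correlation, which is an unlikely premise for a crossover.

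All of this assumes zero-inflated lognormal times and a two-sided 5% level. The planned test is conservative, so the issue is lost efficiency and an open choice of method, not validity. It should be corrected, but it does not by itself invalidate the trial.

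**What to change.** Add to the SAP, before any data are examined:

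- Time at SpO2 of 85% or less is compared by a Wilcoxon signed-rank test on each infant's mean side-lying time minus mean semi-elevated time (42 differences), in place of the independent-samples t-test. State how zero differences are handled; the simulations that record this dropped them.
- Shapiro-Wilk is descriptive and does not select the test.
- The effect estimate is the within-infant mean difference in seconds with a paired 95% CI, for example from a bootstrap that resamples infants.
- The number of sessions with any time at or below 85% is reported by position.

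This costs a few sentences, uses a routine test and needs no extra data. The price is that the test addresses the typical within-infant difference rather than the difference in mean seconds, so the mean difference and its CI must be reported alongside the test.

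### The SAP names independent-groups tests and no within-infant test of position for a crossover, so the standard errors are wrong, most likely too large

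*Combined protocol and SAP*

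**What the plan says.** METHOD sets out the within-infant design: "Four bottle-feeding sessions will be tested in each of the newborn: two in the SEP and two in the SLP". STUDY DESIGN calls the trial a randomised crossover in which the first position is drawn from a random table, "then positioning will be changed after each feeding session". It counts the sample by session: "In each of the study positions 84 feeding sessions will be analyzed", 168 in all. METHOD also limits the daily load, "In one day, only two consecutive feeding sessions which will be included to the study", and gives fatigability as the reason.

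The Statistical Analysis Plan names its comparative methods in one sentence: "tests for independent samples, two-way independent mixed ANOVAs as well as chi-squared tests of independency will be computed" (the first of these are t-tests). It names no paired t-test, signed-rank test, McNemar-type test, GEE or infant effect. It does not define the ANOVA factors or the subject unit, and it assigns no test to any outcome.

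The list under WHAT WILL BE ANALYZED? has seven items. One concerns choking: "The position of the baby during feeding and choking episodes". Another, on intake, reads "Differences in the proportion of the volume of eaten food due to the position of the child during feeding". A third, on duration, reads "Differences in feeding times and feeding sessions due to the position of the baby during feeding". The documents give no alpha, target difference, power, SD or within-infant correlation.

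**The concern.** A crossover is run so that each infant serves as its own control. An independent-samples t-test or a chi-squared test of independence treats the SEP and SLP sessions as if they came from unrelated infants. Differences between infants then stay in the error term although the design removes them from the comparison.

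The t-tests and chi-squared tests most naturally serve four of the seven items: choking, proportion eaten, feeding and session duration, and time at SpO2 ≤85%. If the standard errors are too large, real differences between positions are more easily missed, and a null result on choking or desaturation is weaker evidence than it looks. If they are too small, the nominal 5% level is not kept. In neither case can the reported p-values be taken at face value.

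**Working it through.** **Counts.** 42 × 2 = 84 sessions per position and 42 × 4 = 168 in total, as STUDY DESIGN states. There is no power calculation to reproduce.

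**Assumptions.** Two-sided 5% level and total session variance 1, split into infant (vi), infant-by-position (vip), day within infant (vd) and session (ve). None of these values is in the documents.

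**Variance of the SEP-minus-SLP mean difference.**
- Independent t-test on 84 v 84 sessions: 2/84 = 1/42.
- True variance: (2·vip + ve)/42. The infant effect cancels because each infant contributes two sessions to each position. The day effect cancels because the two feeds of a day are in opposite positions.
- Ratio true/assumed = 2·vip + ve. This exceeds 1 only if vip > vi + vd.

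**Base case**, vip = vd = 0, so the ratio is 1 − ρ. The SE is too large by 1/√(1 − ρ), and size = 2Φ(−1.96/√(1 − ρ)). Where the paired test has 80% power (normal approximation), the planned test has Φ(2.8016 − 1.96/√(1 − ρ)); the difference concerned is 2.8016·√((1 − ρ)/42) SD.

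| Assumed ρ | SE too large by | Size, formula | Size, simulated | Difference (SD) for paired power 80% | Planned power there |
|---|---|---|---|---|---|
| 0.1 | 1.05 | 3.9% | 3.8% | 0.41 | 77% |
| 0.3 | 1.20 | 1.9% | 2.1% | 0.36 | 68% |
| 0.5 | 1.41 | 0.6% | 0.7% | 0.31 | 51% |
| 0.7 | 1.83 | 0.03% | 0.06% | 0.24 | 22% |

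The simulation used 40,000 trials of 42 infants × 4 sessions; the paired test on infant means kept 4.9% to 5.2%. At a fixed difference of 2.8016·√(2/84) = 0.432 SD, simulated power is 80% / 84% / 88% / 93% as planned and 82% / 90% / 97% / 99.9% paired.

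**Day effect.** With vi 0.3, vd 0.2 and ve 0.5 the ratio is 0.5: the SE is 1.41 times too large and size is 0.6%. Without the day effect, vi 0.3 gives 1.20 and 1.9%.

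**Choking.** Simulated uncorrected chi-squared test at an assumed 20% rate, with infant SD 0.5 / 1.0 / 1.5 / 2.0 / 2.5 on the logit scale: size 4.8% / 3.7% / 2.5% / 1.7% / 1.1%.

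**ANOVA, if position is the between factor.** One setting (five time points, infant variance 0.2, residual variance 1, so a session-mean correlation of 0.2/(0.2 + 1/5) = 0.5) gives size 0.7% for the position main effect. The position-by-time interaction keeps 5.1% if infants differ only by a constant level. It falls to 3.3% or 1.0% if infants also have their own time profile (correlation 0.1 or 0.3 at each time point after removing level).

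**When the direction reverses.**
- Infant-by-position variation: vi 0.1, vip 0.4, ve 0.5 gives ratio 1.3 and size 8.6%.
- First-versus-second-feed effect d, in units of the session SD. Strict alternation places it entirely in each infant's position difference, with a sign set by the first position. Ratio = (1 − ρ + d²)/(1 + d²/4), which exceeds 1 once d > √(4ρ/3): 0.37 at ρ 0.1, 0.63 at ρ 0.3, 0.82 at ρ 0.5. Simulated size is 6.0% at ρ 0.1, d 0.5, and 6.9% at ρ 0.3, d 0.8. At ρ 0.3, d 0.3 it is still conservative: (0.7 + 0.09)/1.0225 = 0.77, size about 2.6%.

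**Bias.** STUDY DESIGN mentions a random table but no balancing of the starting position. With n1 and n2 infants in the two sequences, an order effect shifts the estimate by d(n1 − n2)/42 in absolute size, for example 6d/42 = 0.14d at 24:18. The estimate is unbiased only on average over the randomisation.

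**The case against.** Three defences deserve an answer.

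First, a mixed ANOVA contains a repeated factor, and position could be that factor. This stands as a possibility. Measurement time is the more natural repeated factor and the word independent points to position as the between factor, but the SAP does not say so. Even on the generous reading, no paired test is named for the four outcomes without a time course. The allocation of t-tests and chi-squared tests to those four is itself an inference, though a reasonable one.

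Second, the likely error is conservative, small at ρ 0.1, and the planned t-test still has 80% to 93% power at 0.432 SD. This limits the size of the point. The starkest contrast, 22% against 80%, belongs to ρ 0.7 and a difference of only 0.24 SD. The documents set no target difference, so no single figure can be called the loss.

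Third, the paired analysis is not the whole answer, because without a sequence term it leaves any order effect in its error. This also stands. At ρ 0.3, an order effect of 0.8 SD and a position difference of 0.35 SD, paired power is 48% without the term and 74% with it.

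Two stronger readings are tempting. A reader might infer that treating 168 sessions as independent is pseudoreplication that inflates false positives. That follows when the treatment varies between infants; here it is balanced within each infant, and the usual effect is the opposite. A reader might equally infer that the error can only be conservative. The documents do not support that either: METHOD raises fatigability, and position alternates at every feed, so an order effect large enough to reverse the direction cannot be ruled out.

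**Conclusion.** The mismatch is plain for the t-tests and chi-squared tests. It extends to the ANOVA only if position is its between factor. Standard errors that are too large, with lost power, are the more likely consequence. This rests on infants differing more in overall level (and by day) than in their response to position, and on any within-day order effect being moderate. The size depends on a within-infant correlation that the documents do not give: negligible near zero, small at 0.1, serious from about 0.3 upwards. The SAP should be changed whichever direction applies, because the infant-level analysis keeps its nominal level in both.

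**What to change.** In the Statistical Analysis Plan, replace the independent-groups tests of position with infant-level analyses, and state which applies to each of the seven items.

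- **Proportion eaten, feeding and session duration, time at SpO2 ≤85%:** average the two sessions per position and analyse the 42 SEP-minus-SLP differences with a paired test adjusted for randomised sequence. That is, regress the difference on a sequence indicator coded −1/+1 and test the intercept. Give a rank-based version for use if the differences are non-normal.
- **SpO2, HR and alertness:** do the same on a pre-specified change from the pre-feeding measurement (A in STUDY DESIGN) to one named time point.
- **Choking:** analyse the within-infant difference in the number of choking sessions, or use GEE clustered on infant with small-sample-corrected robust standard errors and an order term.
- **Any ANOVA that is kept:** name its factors and subject unit.
- **Reporting:** describe the sample as 42 infants contributing 168 sessions.

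A mixed model with only a random infant intercept is not an adequate substitute. Its simulated size is 13.4% in the infant-by-position case above and 2.8% in the day-effect case.

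The cost is SAP wording, a little more analysis work and one degree of freedom for sequence (40 instead of 41). No new data or infants are needed.
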